Diabetes mellitus (DM) and chronic kidney disease (CKD) represent pandemic diseases and a major public health concerns because of their prevalence and poor cardiovascular prognosis (1-3). DM is the most common cause of CKD and up to 40% of diabetic patients develop CKD (4). CKD was present in approximately one-third of patients with NSTEMI-ACS and was a powerful independent predictor of subsequent mortality (5). Importantly, patients with DM or CKD have a high thrombotic milieu and frequently experience recurrent atherothrombotic events (6-11). Multiple mechanisms may contribute to these observations, including accelerated platelet turnover rates (12,13). These observations underscore the importance of antiplatelet therapy for prevention of atherothrombotic recurrences in these high-risk patients. Clopidogrel is the most widely used platelet P2Y₁₂ receptor inhibitor. However, despite its clinical benefit, patients with DM and CKD frequently experience recurrent atherothrombotic events. The high atherothrombotic recurrence rates in DM and CKD patients are partly due to the inadequate response to antiplatelet agents, in particular clopidogrel, which is enhanced with the co-existence of these disorders (14-17). Therefore, identifying antiplatelet agents with more favorable pharmacokinetic (PK) and pharmacodynamics (PD) profiles is of key importance.

Ticagrelor represents an attractive strategy especially in high-risk patients, such as those with DM and/or CKD (18-20). Ticagrelor, a cyclopentyltriazolopyrimidines, is an oral, reversible, non-competitive P2Y₁₂ receptor inhibitor with rapid onset and offset of action and provides a stronger and more consistent platelet inhibition than clopidogrel (21-23). Although ticagrelor is a direct acting agent, ~30% of its effects are attributed to a metabolite (AR-C124910XX) derived from hepatic metabolism (23). In the large scale phase III PLATO (Platelet Inhibition and Patient Outcomes) trial conducted in ACS patients, ticagrelor, in addition to

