- A. standard dose (90mg twice daily of ticagrelor) for 7-10 days (phase 1) and then cross-over to low dose (60mg twice daily of ticagrelor) for 7-10 days (phase 2)
- B. low dose (60mg twice daily of ticagrelor) for 7-10 days (phase 1) and then cross-over to standard dose (90mg twice daily of ticagrelor) for 7-10 days (phase 2).

After the 2 phases of treatment (maximal treatment period 20 days) patients will resume their standard DAPT with aspirin and clopidogrel (end of study treatment).

[figure not shown]
After 7-10 days of treatment, patients will come for their blood sampling in the morning hours. In particular, patients will not assume their scheduled morning dose of study medication to allow assessment of trough levels of platelet reactivity. Patients will be administered the dose of the randomized treatment while at the clinic and blood sampling will be collected after 2 hours

in order to assess peak levels of platelet reactivity. After completing the first phase of the randomized assignment, patients will initiate the second phase and start assuming assigned medication 12 hours the last dose.

Blood for sampling will be collected at the following visits (a total of 5 assessments at 3 visits):

- a) baseline (24 hours after last clopidogrel MD): PD assessments
- b) after 7-10 days of ticagrelor therapy (phase 1-pre-crossover): PK and PD assessment will be assessed to define trough (12 ± 2 hours after last ticagrelor dose) and peak (2 hours after ticagrelor administration) activity
- c) after 7-10 days of ticagrelor therapy (phase 2-post-crossover): PK and PD assessment will be assessed to define trough (12 ± 2 hours after last ticagrelor dose) and peak (2 hours after ticagrelor administration) activity.

A flow diagram of the study is presented below.

Blood sampling: Peripheral venous blood samples (20 mL) will be drawn through a short venous catheter inserted into a forearm vein and collected in citrate and serum tubes as appropriate for assessments. The first 2-4 mL of blood will be discarded to avoid spontaneous platelet activation.

Laboratory assessments

1. Whole blood vasodilator-stimulated phosphoprotein (VASP)
2. VerifyNow P2Y12 point of care testing
3. Light-transmittance aggregometry (LTA)
4. Thromboelastography
5. Reticulated Platelets (RPs)

6. Serum thromboxane B2
7. PK assessment

Description of laboratory assays

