- 7) *Pharmacokinetic (PK) assay*: Determination of plasma concentration of ticagrelor and its active metabolite (AR-C124910XX) will be assessed from blood samples taken at the same time points of PD analysis as previously described [40]. Blood samples for measurement of drug concentrations will be drawn through the same cannula used for PD sampling. The blood will be taken into lithium heparin tubes and placed on ice until centrifugation (2800 rpm, 4°C, 10 min) within 30 min of sampling to collect the plasma, which will be transferred to plain polypropylene tubes and frozen upright at or below -20°C until analysis.

Primary and secondary objectives

The primary end point is the level of on-treatment platelet reactivity as assessed by VASP-PRI after treatment with ticagrelor 90mg bid on top of aspirin (81mg/day) for 7-10 days. The primary hypothesis of our study is that in DM patients the presence of CKD is associated with lower platelet inhibition (assessed by PRI determined by VASP-P) compared with those without CKD.

Additional objectives include:

- 1) The comparison of PD measures following administration of ticagrelor 90 mg between CKD and non-CKD groups at each time point assessed with PRU determined by the VerifyNow P2Y12 assay, 5 and 20 µM ADP-induced platelet aggregation by LTA and clot kinetic assessed by CORA[®] system.

- 2) The comparisons of level of platelet reactivity as assessed by multiple assays after treatment with ticagrelor 60 mg bid (on top of aspirin 81mg/day) for 7-10 days between the CKD and non-CKD groups.
- 3) The comparison of plasma concentrations of ticagrelor and its metabolite between the DM patients with and without CKD after 7-10 days of ticagrelor (60 and 90 mg) treatment.
- 4) The comparison of platelet inhibition by standard dose (90mg twice daily) versus low dose (60mg twice daily) of ticagrelor in DM patients with or without CKD.
- 5) The comparison of the rates of high on-treatment platelet reactivity (HPR), defined as VASP-PRI $\geq 50\%$, PRU > 208 , 5 μM ADP-induced maximal platelet aggregation $\geq 46\%$ or ADP induced MA > 47 (41,42).
- 6) To evaluate whether response to ticagrelor varies with the proportion of RPs in DM patients according to the CKD status.
- 7) To assess the effects of different levels of P2Y₁₂ inhibition with thromboxane levels.
- 8) The comparison of PD and PK measures according to the CKD classification based on markers of kidney damage (ACR).

Sample Size Computation and Power Analysis

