
The primary hypothesis of our study is that in DM patients the presence of CKD is associated with lower platelet inhibition compared with those without CKD after administration of ticagrelor 90 mg bid. Under the assumption of 10% absolute difference in mean PRI between CKD and non-CKD groups, with a common standard deviation of 13.0% a sample size of 37 patients per group will allow to detect a difference in platelet aggregation between the two

cohorts with a 90% power and two-sided $\alpha=0.05$ (22). Considering the two cohorts (CKD and non-CKD), 74 patients with a valid primary end point data will be needed. Assuming a 40% rate of invalid results due to hemolysis or drop-out, up to 102 patients will need to be randomized in the study. We anticipate to consent approximately 115 patients in order to reach the target number of patients. We have chosen a 10% absolute increase of PRI by VASP-P as reference value since this has been associated with a difference in clinical outcomes (43).

Statistical analysis plan

Categorical variables will be expressed as frequencies and percentages. Continuous variables will be presented as mean \pm SD or median [IQR] when appropriate. Continuous variables will be analyzed for normal distribution with the Kolmogorov-Smirnov test. Student's t-test will be used for comparison of normally distributed continuous variables. Wilcoxon test or Mann-Whitney's U test will be used for comparisons of continuous variables not following a normal distribution. An analysis of covariance (ANCOVA) method with a general linear model, using baseline variables significantly different between groups as covariates, will be used to evaluate the overall difference between groups and all between-groups comparisons, in line with other PK and PD studies (22,24). Analysis of variance (ANOVA) will be used to evaluate intragroup comparisons. In line with recommendations for cross-over study designs, treatment effects will be evaluated considering the functional parameters observed in the overall patient population after the treatment regardless of the sequence in which patients received treatment. Patients who will successfully complete at least one treatment phase of the study will be considered for comparisons. The absolute between-treatment mean differences and 95% confidence intervals will be estimated in the two groups. In order to perform an unbiased

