estimation of the treatment effect, period and sequence effects, which may occur in crossover studies, will be evaluated. A p-value <0.05 will be considered statistically significant. Statistical analysis will be performed using a SPSS v22.0 software.

Publication Strategy/Additional Information

This study will be performed at the University of Florida Health Science Center at UF Health - Division of Cardiology. Patients will be recruited and consented at the Cardiology clinics in the UF Health system. Patients will be screened by cardiology research, who will verify that all candidates meet inclusion criteria. Subjects will be identified with a number and data collection sheets will all be stored in a locked area. Data will be kept for 6 years after enrollment ends to comply with HIPAA regulations. Patients will receive a handout with the names and telephone numbers of the doctors involved in the study. Patients will sign an informed consent relating to the study. Study subjects will be identified first (months 1-18): we expect to enroll 4-5 subjects monthly and complete enrollment in 18 months (total: 82 subjects enrolled). Months 19-20 will be implied for statistical analysis and months 21-22 for manuscript preparation.

We anticipate no major problems with the described protocol since the approach is a straight forward prospective study and is based on well-established methods. However, since there is limited experience with to define platelet function in this specific subset, variability may be higher than expected and we cannot currently perform a detailed sample size calculation. We anticipate adding this to the protocol after inclusion of the study population has been completed. If the sample size after one year is estimated to be too small, additional patients will be included. This approach is in agreement with recommendations for pilot investigations (44).

Possible Discomforts and Risk

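### The primary CKD comparison on 90 mg combines phase 1 and phase 2 values with no sequence term, and the planned period and sequence check is not tied to it

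*Combined protocol and SAP*

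**What the plan says.** - **Research design.** Patients are split by CKD status and, within each group, randomised 1:1 to 90 mg then 60 mg (sequence A) or 60 mg then 90 mg (sequence B), 7-10 days per phase. They enter on at least 30 days of clopidogrel (Study Population). The first sample is "baseline (24 hours after last clopidogrel MD): PD assessments". Phase 2 starts 12 hours after the last phase 1 dose. No washout is described at entry or between phases.
- **Primary and secondary objectives.** "The primary end point is the level of on-treatment platelet reactivity as assessed by VASP-PRI after treatment with ticagrelor 90mg bid". No phase is named.
- **Sample Size Computation and Power Analysis.** The target is 10 PRI points, CKD against non-CKD. The plan then gives its size: "with a common standard deviation of 13.0% a sample size of 37 patients per group".
- **Statistical analysis plan.** "treatment effects will be evaluated considering the functional parameters observed in the overall patient population after the treatment regardless of the sequence". The between-group ANCOVA takes as covariates only those baseline variables found to differ significantly; neither sequence nor phase is named. One completed phase is enough for inclusion. The section ends by saying that period and sequence effects will be evaluated so that the treatment effect is estimated without bias. It gives no model, no test and no consequence, and does not mention the CKD contrast.
- **Background.** High recurrence rates in DM and CKD are described as "partly due to the inadequate response to antiplatelet agents, in particular clopidogrel, which is enhanced with the co-existence of these disorders".

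**The concern.** For a 90 mg value, sequence and phase are the same factor: every sequence A value is from phase 1 and every sequence B value from phase 2. The two kinds of value differ in what came before (clopidogrel or 60 mg ticagrelor) and in time on study. If mean PRI on 90 mg differs between phases for any reason, the CKD difference is undisturbed only when both CKD groups have the same phase mix.

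The inclusion rule lets the mix drift. Loss before the phase 1 sample removes the primary value in both sequences. Loss after it removes the value in sequence B only, because sequence A has already supplied its 90 mg sample. If later loss is more common in one CKD group, that group's primary data lean towards phase 1. CKD status is not randomised, so equal loss cannot be presumed. Even with an equal mix, an unmodelled phase shift adds noise.

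A second route is a clopidogrel effect that persists into phase 1 and differs by CKD. That one would survive perfect sequence balance.

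**Working it through.** **1. The plan's own figure.** Inputs from the sample size section: difference 10, SD 13, power 90%, two-sided 0.05. Normal formula: 2 × (13 × (1.960 + 1.282) / 10)² = 35.5, so 36. Noncentral-t power is 89.6% at 36 and 90.4% at 37 per group. The stated 37 reproduces. The standard error of the CKD difference is 13 × √(2/37) = 3.02 points.

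**2. The primary contrast does pool phases.** With 1:1 sequences, 37 evaluable patients per CKD group supply only 18 or 19 values from any one phase. A comparison of 18 with 19 has about 62% power. The stated size is reached only by combining phases.

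**3. Bias formula.** Let w be the share of a group's 90 mg values taken in phase 1, and r its phase 1 minus phase 2 shift in PRI (subscript C for CKD, N for non-CKD).

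Bias in the CKD difference = w_C r_C − w_N r_N. With a common shift r this is (w_C − w_N) × r.

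The documents give no value for r. Shifts of 2 and 5 points are assumed below.

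**4. Drift from loss.** If a fraction d of patients is lost after the phase 1 sample, w = 0.5 / (0.5 + 0.5(1 − d)) = 1/(2 − d). The plan allows 40% for invalid results and drop-out together, not split by phase or group, so 40% is used here as a high value.

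- d = 0.10 gives w = 0.526; d = 0.40 gives w = 0.625.
- 40% in one group against 10% in the other gives w_C − w_N = 0.099.

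**5. Chance imbalance.** The randomisation method is not stated. Under simple randomisation the SD of w_C − w_N is √(2 × 0.25/37) = 0.116, a 95% range of ±0.23. This is random error with expectation zero.

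| Difference in mix | Shift 2 points | Shift 5 points |
|---|---|---|
| 0.099 (loss 40% v 10%) | 0.20 | 0.49 |
| 0.20 (60:40 v 40:60) | 0.40 | 1.00 |
| 0.23 (edge of chance range) | 0.46 | 1.14 |

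A bias of 0.5 or 1.0 point raises the two-sided type I error from 5% to 5.3% or 6.3% (normal approximation, SE 3.02).

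**6. Noise.** If 13 is the SD within a phase, a 5-point shift with an even mix adds 0.25 × 5² = 6.25 to the variance: √(169 + 6.25) = 13.24.

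**7. Residual effect differing by CKD (hypothetical).** With w = 0.5 in both groups, the bias is half the difference in residual effect. Assumed differences of 1, 2 and 4 points give 0.5, 1.0 and 2.0 points, and type I error of 5.3%, 6.3% and 10.2%. If less effect remains in CKD, the bias favours the primary hypothesis.

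**8. With a sequence term added, 37 per group.**

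- Power is 90.4% with balanced sequences, and 89.3% if 22/37 and 15/37 of the values come from phase 1.
- The CKD difference within one sequence has SE 13 × √(1/18 + 1/19) = 4.28, so a 95% half-width of about 1.96 × 4.28 = 8.4 points.
- The CKD-by-sequence interaction has SE 4.28 × √2 = 6.05. Power is 13% for a 5-point interaction and 38% for a 10-point one.

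**The case against.** - **The pooling sentence speaks of treatment effects, most directly 90 mg against 60 mg.** If that phrase covers the CKD contrast, so does the promised period and sequence check a few lines later; if not, the sentence does not itself show pooling in the primary analysis. This is fair, and it is why the point rests on the unnamed phase and the 37 per group. It also means that sequence is not ignored. The shortfall is a check with no model, no consequence and no stated link to the primary contrast.
- **Allocation is 1:1 within each CKD group.** Expected imbalance at randomisation is therefore zero. This stands: only chance or unequal loss creates a difference in mix, and the resulting sizes are small.
- **A reader might infer that the plan itself says residual clopidogrel effect differs by CKD.** It does not. The Background says that response to clopidogrel is poorer when the two diseases coexist, and nothing about what remains after 7-10 days of ticagrelor. The remainder could be zero. The Background's remark on faster platelet turnover adds little: by their titles, its two citations concern type 2 diabetes, which both groups have, and dialysis, while patients on hemodialysis are excluded.
- **Baseline PRI, measured on clopidogrel, may enter the ANCOVA.** It would do so if it differs significantly. That is partial protection and depends on a test result.
- **A sequence term does not cure a residual effect that depends on CKD.** Correct. With balanced sequences it leaves the CKD estimate unchanged.

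**Conclusion.** The point holds as a gap in the primary model that costs almost nothing to close. It is not evidence that the primary result will be biased. The documents establish that 90 mg values with different preceding treatment are combined, that no sequence or phase term is named for the CKD contrast, and that the inclusion rule lets the phase mix drift. The size is assumed throughout: with a 5-point phase shift, about 0.5 point for loss of 40% against 10%, and 1 point for a 60:40 against 40:60 mix, compared with a target of 10 and a standard error of 3.02.

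Two stronger readings are not supported. The first is that the primary comparison will report a clopidogrel difference as a ticagrelor one; that needs a residual effect, and a CKD difference in it, that the documents never state. The second is that a CKD difference seen only in sequence A should be barred from attribution to ticagrelor. With about 62% power in each sequence, a true and constant 10-point difference would be significant in A alone about 0.62 × 0.38 = 24% of the time. Sequence B's 90 mg phase also follows 60 mg, so comparing sequences cannot separate residual clopidogrel from 60 mg carry-over.

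**What to change.** In the Statistical analysis plan, specify the primary model as VASP-PRI on 90 mg = CKD group + randomised sequence (A or B), and say that this is how period and sequence are handled for the CKD contrast. Preferably also fix baseline PRI as a covariate in advance, so that its inclusion does not hang on a significance test.

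Report the CKD difference within each sequence, with 95% confidence intervals, as a descriptive sensitivity analysis. State alongside it that:

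- these estimates are imprecise (interaction SE about 6 points);
- they cannot separate residual clopidogrel from 60 mg carry-over;
- the additive term corrects an unequal sequence mix, not a residual effect that depends on CKD.

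Attach no decision rule to the sequence-specific results. Report the number of valid 90 mg values by sequence and CKD group, so that drift is visible.

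The cost is wording and one degree of freedom for the sequence term; power stays at about 90%. No change to the treatment schedule is involved.

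### The SAP names no method that uses one-phase patients in the 60 mg versus 90 mg comparison, and plans no estimate of how the dose effect differs by CKD (secondary aims only; a cheap improvement)

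*Combined protocol and SAP*

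**What the plan says.** On who is analysed, the Statistical analysis plan states: "Patients who will successfully complete at least one treatment phase of the study will be considered for comparisons".

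On method, it lists Student's t-test for normally distributed variables, Wilcoxon or Mann-Whitney tests otherwise, and ANCOVA for between-group comparisons. For comparisons within a group: "Analysis of variance (ANOVA) will be used to evaluate intragroup comparisons". It does not say whether that ANOVA is paired, repeated-measures or independent.

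On the crossover, "treatment effects will be evaluated considering the functional parameters observed in the overall patient population after the treatment regardless of the sequence" in which treatment was received. The next relevant sentence opens "In order to perform an unbiased" and continues "estimation of the treatment effect, period and sequence effects, which may occur in crossover studies, will be evaluated". No model is given for this.

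On the dose estimate: "The absolute between-treatment mean differences and 95% confidence intervals will be estimated in the two groups". Nothing is said about comparing those two differences with each other.

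Significance and Rationale lists as an open question whether CKD affects PK/PD profiles under different ticagrelor doses, and Study aims takes this up for 60 mg and 90 mg. In Primary and secondary objectives, additional objectives 1 to 3 compare CKD with non-CKD on 90 mg, on 60 mg, and for plasma concentrations on both. Objective 4 compares the two doses.

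**The concern.** There are two gaps, both in the secondary aims.

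First, the inclusion rule and the named tests do not fit together for the dose comparison. A paired t-test, a signed-rank test or a standard repeated-measures ANOVA needs both phases, so a patient with only one valid phase is lost. An independent-sample test keeps that patient but discards the within-patient pairing that a crossover is run to obtain. The plan expects losses from hemolysis and drop-out, and a single hemolysed sample is an obvious way to become a one-phase patient.

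Second, the plan yields a dose difference in each group but no difference between those differences. Without it, readers may compare the two results by eye and take significance in one group but not the other as evidence that CKD changes the dose effect.

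At stake are some precision in the dose comparison and a direct estimate bearing on the open question in the rationale. The primary comparison needs one 90 mg value per patient and no pairing, so it is untouched.

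**Working it through.** **The plan's own figure.** Sample Size Computation and Power Analysis assumes a difference of 10 PRI points, SD 13, two-sided alpha 0.05 and 90% power, giving 37 per group. A two-sample t-test gives 89.6% power at 36 and 90.4% at 37, so 37 reproduces. This is the only powered comparison; no figure is given for the dose comparison or the dose-by-CKD difference.

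**Inputs from the plan.** SD 13; "up to 102 patients will need to be randomized in the study"; "74 patients with a valid primary end point data will be needed". With equal CKD groups that is 102/2 = 51 randomized and 74/2 = 37 valid per group, a valid share of 37/51 = 0.725. The plan's stated 40% loss would leave about 31 of 51; its own counts are used here.

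**Inputs assumed.** The within-patient correlation r is not in the documents; results are shown for r = 0.3 / 0.5 / 0.7. The valid share at 60 mg is taken as equal to that at 90 mg.

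**How many one-phase patients.** If losses are independent between phases:
- complete pairs: 51 × 0.725² = 26.8, about 27 per group;
- one dose only: 51 × 0.725 × 0.275 = 10.2, about 10 per group for each dose.

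Given 51 and 37, the number of pairs can range from 37 + 37 − 51 = 23 (nobody loses both phases) to 37 (every loss removes both).

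**Standard error of the dose difference in one CKD group.**
- Pairs only: 13 × √(2(1−r)/27) = 2.96 / 2.50 / 1.94.
- Mixed model, 27 pairs plus 10 per dose spread evenly over phases: 13 × √(2 / (27/(1−r) + 10)) = 2.64 / 2.30 / 1.84.
- Reduction: 10.9 / 8.1 / 5.1%.

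The second formula is the generalised least squares result with r known and with dose, period, sequence, CKD and dose-by-CKD fitted. It adds the information in the paired differences to that in the one-phase patients.

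**Sensitivity of the gain** (same least squares calculation):
- all one-phase patients have phase 1 only: SE 2.68 / 2.33 / 1.86, a reduction of 9 / 7 / 4%;
- as above, with period and sequence effects allowed to differ by CKD group: SE 2.73 / 2.37 / 1.88, a reduction of 8 / 5 / 3%;
- limit of 23 pairs plus 14 per dose: reduction of 16 / 12 / 8%;
- limit of 37 pairs and no one-phase patients: SE 2.53 / 2.14 / 1.66 by either method, no gain.

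**Dose-by-CKD difference.** The groups are independent, so with 37 pairs in each:
- SE = 13 × √(4(1−r)/37) = 3.58 / 3.02 / 2.34;
- 95% CI half-width, 1.96 × SE = 7.0 / 5.9 / 4.6 points;
- difference detectable with 80% power, (1.96 + 0.842) × SE = 10.0 / 8.5 / 6.6 points.

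With 27 pairs plus the one-phase patients the SE is 3.73 / 3.25 / 2.60, against 4.19 / 3.54 / 2.74 from the pairs alone. The primary effect is itself assumed to be 10 points, so this supports an interval and not a powered test.

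**The case against.** Four points on the other side carry weight.

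The one-phase rule is not limited to the dose comparison. In the primary analysis and in objectives 1 to 3, a one-phase patient contributes fully at the dose received, and the rule may be meant mainly for those. A reader might infer that the plan promises to use such patients in the dose contrast and then breaks the promise; the text does not go that far. What stands is that the rule sits among the treatment-effect sentences and that no named test can honour it there without giving up the pairing.

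No numbered objective asks for a dose-by-CKD difference. CKD versus non-CKD at each dose answers the stated aim on a plain reading, so the plan cannot be said to leave an objective without an analysis. The difference would inform that aim; it is not required by it.

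The two groups most naturally means CKD and non-CKD, since the sample size section speaks of those two cohorts. On that reading the contrast and its standard error can be derived from the two planned estimates, but only from whichever patients entered them.

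A reader might also infer that the dose difference will be unadjusted for period. The plan says that period and sequence effects will be evaluated for the sake of an unbiased estimate. Sequence is randomized 1:1 within each CKD group, so with balanced pairs a period effect cancels from the mean dose difference. What is missing is the model, not the intention.

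**Conclusion.** The point holds as a cheap improvement to the secondary analyses. The plan names no method that uses one-phase patients and keeps the pairing in the dose comparison, and it plans no estimate of how the dose effect differs by CKD.

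The precision at stake is modest: a per-group standard error 11/8/5% smaller in the central scenario, zero if losses always affect both phases, and more than 11% only near the arithmetic limit where no patient loses both. These figures rest on the assumed correlation, equal validity at the two doses, equal CKD groups and the assumed pattern of losses. None of these is in the documents.

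A reader might infer that the doses will be compared as independent samples. That would give an SE of 13 × √(2/37) = 3.02 against 2.53/2.14/1.66 for 37 pairs, so intervals 1.2 to 1.8 times wider. The documents do not support this: the design is a crossover, the ANOVA is for intragroup comparisons and period effects are to be examined, so a paired analysis is the natural reading. Nor is there any consequence for the primary comparison or its sample size.

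**What to change.** For each continuous PD and PK measure, at trough and at peak, replace the intragroup ANOVA or t-test for dose with a linear mixed model. Use fixed effects for dose, period, sequence, CKD and dose-by-CKD, and a random patient effect. Log-transform PK and skewed measures. Include every patient with at least one valid phase and state the missing-at-random assumption. Keep the planned tests on complete pairs as a sensitivity analysis, and keep the ANCOVA for CKD versus non-CKD at a single dose.

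Report the period-adjusted dose difference overall and in each CKD group, with 95% CIs. Report the dose-by-CKD difference with its 95% CI, labelled exploratory, unpowered and associational (CKD is not randomized), and make no significance claim for it. State that the two groups are CKD and non-CKD, if that is meant, and whether period and sequence effects are taken as common to both.

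The cost is SAP wording and a little more analysis of data already collected, with no extra patients, visits or samples. The downsides are reliance on missing at random and additional unpowered estimates across several assays.

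### One unrestricted p<0.05 rule covers eight additional objectives (roughly 30 to 90 or more comparisons) with no testing order, and only the ACR analysis is labelled exploratory

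*Combined protocol and SAP*

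**What the plan says.** The section on primary and secondary objectives names one primary end point: "The primary end point is the level of on-treatment platelet reactivity as assessed by VASP-PRI after treatment with ticagrelor 90mg bid", compared between patients with and without CKD. The sample size section sizes the trial for that comparison only. It takes a true gap of 10 PRI points, "with a common standard deviation of 13.0% a sample size of 37 patients per group". Power is set at 90% and alpha at 0.05, two-sided.

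Eight additional objectives follow:

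- Objective 1: other platelet measures on 90 mg ("The comparison of PD measures following administration of ticagrelor 90 mg between CKD and non-CKD groups at each time point").
- Objective 2: platelet reactivity by several assays on 60 mg.
- Objective 3: plasma levels of ticagrelor and its metabolite on both doses.
- Objective 4: 90 mg against 60 mg.
- Objective 5: rates of high platelet reactivity under four cut-offs.
- Objectives 6 and 7: reticulated platelets and thromboxane.
- Objective 8: the pharmacodynamic and pharmacokinetic comparisons repeated with CKD defined by ACR.

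The Statistical analysis plan section describes the methods for all comparisons together and ends with "A p-value <0.05 will be considered statistically significant". It contains no adjustment, no order and no statement that the additional objectives are descriptive. The one limiting label is under Research design, where the ACR classification is called exploratory. Objective 8 does not repeat that label, and the significance rule does not exempt it.

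**The concern.** The threshold is the one used to size a single test, but as written it applies to every comparison under every objective. If the primary comparison is null, the plan still allows a CKD or dose effect to be called statistically significant from whichever assay, dose and sampling time falls below 0.05. Labelling one analysis exploratory also suggests that the others are not.

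The section on possible benefits says that differences in antiplatelet profile may prompt a larger clinical study. A chance finding presented as significant could therefore affect what is done next.

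**Working it through.** **1. The plan's own figure.** For a difference of 10, SD 13, two-sided alpha 0.05 and 90% power:

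n per group = 2 × (1.960 + 1.282)² × 13² / 10² = 2 × 10.51 × 1.69 = 35.5, so 36 by the normal approximation.

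The t-test calculation gives 36.5, so 37. The stated 37 per group reproduces, with power 90.4% by the t-test. It covers one comparison; no additional objective has a sample size or alpha of its own.

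**2. Counting comparisons.** The documents give no count, so this one is a reading of them. Inputs:

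- Five platelet measures: VASP-PRI, PRU, LTA with 5 µM ADP, LTA with 20 µM ADP, and the CORA panel taken as one. These are four assays, because LTA is one assay at two agonist concentrations.
- Two analytes, two doses, two sampling times (trough and peak, from Research design) and two CKD groups.
- Objective 5 is read as CKD against non-CKD. Objectives 6 and 7 are left out because the text does not define their tests.

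| Objective | Full crossing | Narrowest reading considered |
|---|---|---|
| 1 | 4 measures × 2 times = 8 | 8 |
| 2 | 5 × 2 times = 10 | 5 × 1 time = 5 |
| 3 | 2 analytes × 2 doses × 2 times = 8 | 2 × 2 × 1 = 4 |
| 4 | 5 × 2 times × 2 groups = 20 | 5 × 1, groups pooled = 5 |
| 5 | 4 cut-offs × 2 doses × 2 times = 16 | 4 × 2 × 1 = 8 |
| 8 (ACR) | 5 × 2 × 2 + 8 = 28 | omitted |
| Total | 90 | 30 |

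The full crossing without ACR is 90 − 28 = 62. Adding R, K and Angle from the CORA panel raises 90 to 126.

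**3. Mean number of false positives if every null hypothesis is true.** This is m × 0.05 whatever the correlation: 30 × 0.05 = 1.5; 62 × 0.05 = 3.1; 90 × 0.05 = 4.5.

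**4. Chance of at least one.** Under independence it is 1 − 0.95^m. With a common pairwise correlation ρ between normal test statistics it is

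1 − ∫ φ(u) [Φ((1.96 − √ρ u)/√(1−ρ)) − Φ((−1.96 − √ρ u)/√(1−ρ))]^m du,

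evaluated numerically. The documents give no correlation, so ρ is an assumption and is shown as a range.

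| Tests | Mean | ρ = 0 | ρ = 0.5 | ρ = 0.7 | ρ = 0.9 |
|---|---|---|---|---|---|
| 30 | 1.5 | 0.79 | 0.51 | 0.34 | 0.17 |
| 62 | 3.1 | 0.96 | 0.67 | 0.43 | 0.20 |
| 90 | 4.5 | 0.99 | 0.75 | 0.48 | 0.22 |

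**5. Shape of the distribution.** With 90 tests the median number of false positives is 2 at ρ = 0.5 and 0 at ρ = 0.7. The chance of three or more is 0.83 under independence, 0.28 at ρ = 0.7 and 0.15 at ρ = 0.9. With correlated assays, most of the mean comes from a minority of trials with many false positives.

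**The case against.** The strongest reply is that this is a small mechanistic study with one named primary end point and hypothesis, and with alpha and power set for that alone. The other objectives are called additional, the publication section refers to recommendations for pilot investigations, and the trial is said not to be designed to assess clinical benefit. The plan already includes mean differences with 95% confidence intervals for the dose comparison. A reader could take the secondary results as supportive without being told. That is a fair account of the likely intent, but the plan does not say it, and the rule it does state points the other way.

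Several points about size also stand:

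- A reader might infer that at least 90 comparisons are planned. The documents do not support this as a minimum. Only objective 1 specifies each time point, the dose comparison could be pooled over CKD groups, and 28 of the 90 belong to the ACR analysis already called exploratory.
- A reader might infer that any one trial should be expected to show several false positives. The 4.5 is a mean. The assays use the same patients and visits, and most measure the response to ADP, so correlation may be high and the commonest result may be none.
- The high-reactivity tests may run below 5% size. Assuming Fisher's exact test at 37 per group, the size is about 0.3% at an assumed 5% rate and 1.5% at 10%. Dropping objective 5 altogether still leaves 30 − 8 = 22 to 90 − 16 = 74 tests, with a mean of 1.1 to 3.7.
- Dose may truly affect platelet inhibition, so a null for objective 4 may be unrealistic. Without it, the full crossing is 70 tests and the mean is 3.5.

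A reader might also infer that the trial's primary conclusion is at risk. It is not: adding secondary tests does not change the error rate of a single prespecified primary test. The primary's unstated sampling time (trough or peak) is a separate matter.

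**Conclusion.** The point holds as a cheap improvement to the plan. The significance rule reaches every additional objective, and nothing except the exploratory label on the ACR classification restrains the claims that may follow.

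Even on the narrowest count with an assumed correlation of 0.9, the chance of at least one false significant result is about 17%, more than three times the nominal 5%. On wider counts or with weaker correlation it is far higher. These figures assume that all null hypotheses are true, that each test has its full 5% size, and that one common correlation applies. The count itself rests on how the objectives are read. The conclusion does not depend on choosing one reading, because no count or correlation considered brings the error rate near 5%.

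**What to change.** In the Statistical analysis plan section, replace the general threshold sentence with one that:

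- limits the claim of statistical significance at two-sided 0.05 to the primary VASP-PRI comparison between CKD and non-CKD patients on 90 mg;
- optionally names one key secondary, tested at 0.05 only if the primary is significant (for example PRU on 90 mg at the sampling time specified for the primary);
- states that all other objectives are reported as estimates with 95% confidence intervals, with any p-values nominal and labelled exploratory.

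Objective 8 should carry the exploratory label already given under Research design.

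A ban on secondary p-values is not needed. A Bonferroni correction is possible but would set the level at 0.05/30 = 0.0017 to 0.05/90 = 0.00056, in a trial sized for one test.

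The change is wording only: no patients, visits or assays are affected. The downside is that a secondary finding could no longer be headlined as statistically significant. The change should be made before any results are seen.
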